### **3.7. Data Handling Conventions and Transformations**

The following conventions will be used for the imputation of date of birth when it is partially missing or not collected:

- If only month and year of birth is collected, then “15” will be imputed as the day of birth
- If only year of birth is collected, then “01 July” will be imputed as the day and month of birth
- If year of birth is missing, then date of birth will not be imputed

In general, age (in years) on the date of the first dose of study drug will be used for analyses and presented in listings. If age on first dose date of study drug is not available for a subject, then age derived based on date of birth and the Day 1 visit date will be used instead. If an enrolled subject was not dosed with any study drug, the enrollment date will be used instead of the Day 1 visit date. For screen failures, the date the first informed consent was signed will be used for the age derivation.

Laboratory data (Non-PK) data that are continuous in nature but are less than the lower limit of quantitation (LOQ) or above the upper LOQ will be imputed as follows:

- A value that is 1 unit less than the LOQ will be used to calculate descriptive statistics if the datum is reported in the form of “< x” (where x is considered the LOQ). For example, if the values are reported as < 50 and < 5.0, values of 49 and 4.9, respectively, will be used to calculate summary statistics. An exception to this rule is any value reported as < 1 or < 0.1, etc. For values reported as < 1 or < 0.1, a value of 0.9 or 0.09, respectively, will be used to calculate summary statistics.
- A value that is 1 unit above the LOQ will be used to calculate descriptive statistics if the datum is reported in the form of “> x” (where x is considered the LOQ). Values with decimal points will follow the same logic as above.
- The LOQ will be used to calculate descriptive statistics if the datum is reported in the form of “≤ x” or “≥ x” (where x is considered the LOQ).

Logarithm (base 10) transformation will be applied to HIV-1 RNA data for efficacy analysis. HIV-1 RNA results of ‘No HIV-1 RNA detected’ and “<20 cp/mL HIV-1 RNA Detected” will be imputed as 19 copies/mL for analysis purpose.

Natural logarithm transformation will be used for analyzing concentrations and PK parameters in intensive PK samples. Concentration values that are below limit of quantitation (BLQ) will be presented as “BLQ” in the concentration data listing. Values that are BLQ will be treated as 0 at predose time points and one-half the value of the LOQ at postdose time points for summary purposes.

The following conventions will be used for the presentation of summary and order statistics for intensive PK concentrations:

- If at least 1 subject has a concentration value of BLQ for the time point, the minimum value will be displayed as “BLQ.”
- If more than 25% of the subjects have a concentration data value of BLQ for a given time point, the minimum and Q1 values will be displayed as “BLQ.”
- If more than 50% of the subjects have a concentration data value of BLQ for a given time point, the minimum, Q1, and median values will be displayed as “BLQ.”
- If more than 75% of the subjects have a concentration data value of BLQ for a given time point, the minimum, Q1, median, and Q3 values will be displayed as “BLQ.”
- If all subjects have concentration data values of BLQ for a given time point, all order statistics (minimum, Q1, median, Q3, and maximum) will be displayed as “BLQ.”

PK parameters that are BLQ will be imputed as one-half LOQ before log transformation or statistical model fitting.

### **3.8. Analysis Windows**

#### **3.8.1. Definition of Predose, Postdose, and Study Day for Part 1**

Predose value is defined as the last available off-treatment value collected prior to the first dose of GS-9131 in Part 1 Sentinel cohorts.

Postdose value is defined as any value collected after the first dose of GS-9131 up to the date of the last dose of GS-9131 in Part 1 plus 30 days, and before the first dose date of Part 2 if applicable.

Study Day will be calculated from the first dosing date of GS-9131 in Part 1 Sentinel cohorts as follows:

- For postdose study days: Assessment Date – First Dosing Date + 1
- For days prior to the first dose: Assessment Date – First Dosing Date

Study day 1 is the day of first dose of GS-9131 administration in Part 1 Sentinel cohorts.

#### **3.8.2. Analysis Visit Windows for Part 1**

The nominal visit as recorded on the CRF will be used when data are summarized by visit. Any data relating to unscheduled visits will not be assigned to a particular visit or time point and in general will not be included in summaries. However, the following exceptions will be made:

- An unscheduled visit prior to the first dose of study drug may be included in the calculation of predose value, if applicable.
- Unscheduled visits after the first dose of study drug will be included in determining the maximum postbaseline toxicity grade.
- For subjects who discontinue from the study, early termination (ET) data will be summarized as a separate visit, labeled as “Early Termination Visit”.

Data obtained after the follow-up visit or last dose date plus 30 days (whichever is later) will be excluded from the summaries, but will be included in the listings.

The nominal visits for HIV-1 RNA, laboratory tests and vital signs, CD4 cell count and ECG are summarized in [Table 3-1](#), [Table 3-2](#), and [Table 3-3](#) respectively.

**Table 3-1. Predose and Postdose Visits for HIV-1 RNA**

Cohort	Visit Label
Sentinel Cohort 1	Predose
	Treatment Day 2
	Treatment Day 3
	Treatment Day 7
	Treatment Day 10
	Treatment Day 11
Sentinel Cohort 2	Predose
	Treatment Day 3
	Treatment Day 7
	Treatment Day 10
	Treatment Day 14
	Treatment Day 15

**Table 3-2. Predose and Postdose Visits for Laboratory Tests (Hematology, Chemistry, and Urinalysis), and Vital Signs**

Cohort	Visit Label
Sentinel Cohort 1	Predose
	Treatment Day 7
	Treatment Day 11
Sentinel Cohort 2	Predose
	Treatment Day 3
	Treatment Day 5
	Treatment Day 7
	Treatment Day 10
	Treatment Day 14
	Treatment Day 15

Note: Vital signs for Sentinel Cohort 2 will not be summarized on Day 5 and Day 15, since they were not collected on these days.

**Table 3-3. Predose and Postdose Visits for CD4 Cell Count and ECG**

Cohort	Visit Label
Sentinel Cohort 1	Predose
	Treatment Day 11
Sentinel Cohort 2	Predose
	Treatment Day 10
	Treatment Day 14
	Treatment Day 15

Note: ECG for Sentinel Cohort 2 will not be summarized on Day 14, since they were not collected on these days.

**3.8.3. Selection of Data in the Event of Multiple Records on the Same Day**

Depending on the statistical analysis method, single values may be required for each day. For example, change from predose by visit usually requires a single value.

If multiple valid, nonmissing observations exist on a day, records will be chosen based on the following rules if a single value is needed:

- For predose and postdose HIV-1 RNA, the latest (considering both collection date and time) record(s) on the scheduled visit will be selected. If both “HIV RNA Taqman 2.0” and “HIV RNA Repeat” (ie, the HIV-1 RNA result obtained from an additional aliquot of the original sample) are available with the same collection time, the results from the “HIV RNA Repeat” will be selected for analysis purposes; otherwise, if there are multiple “HIV RNA Taqman 2.0” records with the same collection time, the geometric mean will be taken for analysis purposes.
- For predose of other assessments, the last available non-missing record on or prior to the date and time of the first dose of study drug will be selected, unless specified differently. If there are multiple records with the same time or no time recorded on the same day, the predose value will be the average (arithmetic or geometric mean, as appropriate) of the measurements for continuous data, or the measurement with the lowest severity (eg, normal will be selected over abnormal for safety ECG findings) for categorical data.
- For postdose of other assessments, if there is more than 1 record on the selected day, the average will be taken for continuous data and the worse severity will be taken for categorical data, unless otherwise specified.

## **4. SUBJECT DISPOSITION**

### **4.1. Subject Enrollment and Disposition**

A summary of subject enrollment will be provided by cohort for each country or investigator within a country and overall. The summary will present the number and percentage of subjects enrolled. For each column, the denominator for the percentage calculation will be the total number of subjects analyzed for that column.

A summary of subject disposition will be provided by cohort. This summary will include the number of subjects screened, screen failure subjects who were not enrolled, subjects who met all eligibility criteria and were not enrolled, subjects enrolled, and subjects in the Safety Analysis Set.

In addition, the number and percentage of the subjects in the following categories will be summarized:

- Completed study drug in Part 1 Sentinel cohorts
- Did not complete study drug with reason for premature discontinuation of study drug in Part 1
- Entered into Part 2
- Completed study drug in Part 2
- Did not complete study drug with reason for premature discontinuation of study drug in Part 2
- Completed the study
- Did not complete the study with reason for premature discontinuation of study

For the Safety Analysis Set category, the denominator for the percentage calculation will be the total number of subjects enrolled for each column. For all other categories, the denominator for the percentage calculation will be the total number of subjects in the Safety Analysis Set for each column.

In addition, the total number of subjects who were enrolled, and the number of subjects in each of the disposition categories listed above will be displayed in a flowchart.

Recommended sentence to add for all randomized studies:

The following by-subject listings will be provided by subject identification (ID) number in ascending order to support the above summary tables:

- Reasons for premature study drug or study discontinuation

No inferential statistics will be generated. A data listing of reasons for premature study drug/study discontinuation will be provided.

#### **4.2. Extent of Study Drug Exposure and Adherence**

A subject's extent of exposure to study drug data will be generated from the study drug administration page in the eCRF. Exposure data will be listed.

#### **4.3. Protocol Deviations**

A by-subject listing will be provided for those subjects who did not meet at least 1 eligibility (inclusion or exclusion) criterion. The listing will present the eligibility criterion (or criteria if more than 1 violation) that subjects did not meet and related comments, if collected.

Protocol deviations occurring after subjects entered the study are documented during routine monitoring. Any deviations identified will be evaluated to determine if it justifies excluding the subject from any analysis sets.

## **5. BASELINE CHARACTERISTICS**

### **5.1. Demographics and Baseline Characteristics**

Subject demographic variables (ie, age, sex, race, and ethnicity) and baseline characteristics (body weight [in kg], height [in cm], body mass index [BMI; in kg/m^2]) will be summarized by cohort using descriptive statistics for continuous variables and using number and percentage of subjects for categorical variables. The summary of demographic data will be provided for the Safety Analysis Set.

A by-subject demographic listing will be provided by subject ID number in ascending order.

### **5.2. Baseline Disease Characteristics**

The following baseline disease characteristics will be summarized:

- HIV-1 RNA (copies/mL)
- CD4+ cell count (/μL)
- Mode of infection (HIV risk factors)
- HIV disease status
- eGFRCG (mL/min)

A by-subject listing of baseline disease characteristics will be provided by subject ID number in ascending order.

### **5.3. Medical History**

General medical history data will be collected at screening and listed only.

A by-subject listing of general medical history will be provided by subject ID number in ascending order. The listing will include relevant medical condition or procedure reported term, onset date, ongoing status, and resolution date (if applicable).

## **6. EFFICACY ANALYSES**

Since the study was prematurely discontinued, there was no efficacy data from the randomized cohort. The efficacy analysis will only include the efficacy data from the sentinel cohorts.

Predose and change from Predose in log10 HIV-1 RNA, CD4 cell count, and CD4% will be summarized by visit and cohort for Part 1.

All efficacy data including HIV-1 RNA, CD4 cell count, and CD4 % from the entire study including Part 2 will be listed.

## **7. SAFETY ANALYSES**

Safety data from the Sentinel Cohorts of the study in Part 1 will be summarized for the subjects in the Safety Analysis Set. All safety data collected up to 30 days after the Part 1 Sentinel Cohorts last dose date and before the Part 2 first dose date (if applicable) will be summarized by cohort, unless specified otherwise. All safety data from both Parts of the study will be included in data listings.

### **7.1. Adverse Events and Deaths**

#### **7.1.1. Adverse Event Dictionary**

Clinical and laboratory AEs will be coded using the current version of MedDRA. System organ class (SOC), high-level group term (HLGT), high-level term (HLT), preferred term (PT), and lowest-level term (LLT) will be provided in the AE dataset.

#### **7.1.2. Adverse Event Severity**

Adverse events are graded by the investigator as Grade 1 (mild), Grade 2 (moderate), Grade 3 (severe) or Grade 4 (life threatening) according to toxicity criteria specified in the protocol. The severity grade of events for which the investigator did not record severity will be left as “missing” data listings.

#### **7.1.3. Relationship of Adverse Events to Study Drug**

Study drug related AEs are those for which the investigator selected “Related” on the AE CRF to the question of “Related to Study Treatment.” Relatedness will always default to the investigator’s choice, not that of the medical monitor. Events for which the investigator did not record relationship to study drug will be considered related to study drug for summary purposes. However, by-subject data listings will show the relationship as missing from that captured on the CRF.

#### **7.1.4. Serious Adverse Events**

Serious adverse events (SAEs) will be identified and captured as SAEs if the AEs met the definition of SAEs that were specified in the study protocol. SAEs captured and stored in the clinical database will be reconciled with the SAE database from the Gilead Pharmacovigilance and Epidemiology Department before database finalization.

## **7.1.5. Treatment-Emergent Adverse Events**

### **7.1.5.1. Definition of Treatment-Emergent Adverse Events**

Treatment-emergent adverse events (TEAEs) are defined as 1 or both of the following:

- Any AEs with an onset date on or after the study drug start date and no later than 30 days after permanent discontinuation of the study drug.
- Any AEs leading to premature discontinuation of study drug.

The TEAE definitions will be applied to Part 1 only. AEs onset date will be compared with the Part 1 first dose date and last dose date and premature discontinuation of study drug refers to study drug discontinuation during Part 1. An AE meeting the TEAE criteria will be considered as a TEAE in Part 1. All AE data including Part 2 will be listed.

### **7.1.5.2. Incomplete Dates**

If the onset date of the AE is incomplete and the AE stop date is not prior to the first dosing date of study drug, the month and year (or year alone if month is not recorded) of onset determine whether an AE is treatment emergent. The event is considered treatment emergent if both of the following 2 criteria are met:

- The AE onset is the same as or after the month and year (or year) of the date of first dose of study drug, and
- The AE onset date is the same as or before the month and year (or year) of the date corresponding to the minimum of (1) 30 days after the date of the Part 1 last dose of study drug and (2) Part 2 first dose date if applicable.

An AE with completely missing onset and stop dates, or with the onset date missing and a stop date marked as ongoing or on or after the date of the Part 1 first dose of study drug, will be considered to be treatment emergent. In addition, an AE with the onset date missing and incomplete stop date with the same or later month and year (or year alone if month is not recorded) as the first dosing date of study drug will be considered treatment emergent.

## **7.1.6. Summaries of Adverse Events and Death**

Treatment-emergent AEs will be summarized based on the Safety Analysis Set.

A brief, high-level summary of the number and percentage of subjects who experienced at least 1 TEAE in the categories described below will be provided by cohort in Part 1. All treatment-emergent deaths observed in the study will also be included in this summary. The number and percentage of subjects who experienced at least 1 TEAE will be provided and summarized by SOC, PT, and cohort as follows:

- TEAEs

- Grade 2, 3, or 4 TEAEs
- Grade 3 or 4 TEAEs
- Treatment-emergent study drug-related AEs
- Grade 2, 3, or 4 treatment-emergent study drug-related AEs
- Grade 3 or 4 treatment-emergent study drug-related AEs
- Treatment-emergent SAEs
- Treatment-emergent study drug-related SAEs
- TEAEs leading to premature discontinuation from study drug

Multiple events will be counted only once per subject in each summary. Adverse events will be summarized and listed first in alphabetic order of SOC and then by PT in descending order of total frequency within each SOC. For summaries by severity grade, the most severe grade will be used for those AEs that occurred more than once in an individual subject during the study.

In addition to the above summary tables, all TEAEs, Grade 3 or 4 TEAEs, treatment-emergent study drug-related AEs, Grade 2, 3, or 4 treatment-emergent study drug-related AEs, and treatment-emergent SAEs will be summarized by PT only, in descending order of total frequency.

In addition, data listings for all AEs regardless of Part will be provided for the following:

- All AEs
- Grade 3 and 4 AEs
- SAEs
- Study-Drug-Related SAEs
- Deaths report
- AEs leading to premature discontinuation of study drug

## **7.2. Laboratory Evaluations**

Laboratory data collected during Part 1 of the study will be analyzed and summarized using both quantitative and qualitative methods. Summaries of laboratory data will be provided for the Safety Analysis Set. The analysis will be based on values reported in conventional units. When values are below the LOQ, they will be listed as such, and the imputed value will be used for the purpose of calculating summary statistics as specified in Section 3.7.

A by-subject listing for laboratory test results will be provided by subject ID number and visit in chronological order for hematology, serum chemistry, and urinalysis separately for all data collected from both Parts of the study. Values falling outside of the reference range and/or having a severity grade of 1 or higher on the Gilead Grading Scale for Severity of Adverse Events and Laboratory Abnormalities will be flagged in the data listings, as appropriate.

No formal statistical testing is planned.

### **7.2.1. Summaries of Numeric Laboratory Results**

Descriptive statistics will be provided by Cohort (different dose of GS-9131) for each laboratory test specified in the study protocol as follows:

- Predose values
- Values at each postdose time point
- Change from predose at each postdose timepoint

Predose and postdose values will be defined as described in Section 3.8.1. Change from predose to a postdose visit will be defined as the visit value minus the predose value. Laboratory test results collected at unscheduled visits will be included for the predose and postdose maximum and minimum value selection. The mean, median, Q1, Q3, minimum, and maximum values will be displayed to the reported number of digits; SD values will be displayed to the reported number of digits plus 1.

In the case of multiple values in an analysis window, data will be selected for analysis as described in Section 3.8.3.

### **7.2.2. Graded Laboratory Values**

The Gilead Grading Scale for Severity of Adverse Events and Laboratory Abnormalities will be used for assigning toxicity grades (0 to 4) to laboratory results for analysis. Grade 0 includes all values that do not meet the criteria for an abnormality of at least Grade 1. For laboratory tests with criteria for both increased and decreased levels, analyses for each direction (ie, increased, decreased) will be presented separately.

If there is any laboratory toxicity grading scale overlapping with the normal reference ranges (eg, grade 1 scale overlaps with normal reference ranges), laboratory values that are within the normal range will be grade 0, except for lipid tests.

For triglycerides, LDL, and cholesterol, protocol-specified toxicity grading scale is for fasting test values, so nonfasting lipid results (or lipid results without a known fasting status) will not be graded or summarized by toxicity grades.

### 7.2.2.1. Treatment Emergent Laboratory Abnormalities

Treatment-emergent laboratory abnormalities are defined as values that increase at least 1 toxicity grade from predose at any posedose time point, up to 30 days after Part 1 last dose date or before Part 2 first dose date (if applicable), whichever occurs earlier. If the relevant predose laboratory value is missing, any abnormality of at least Grade 1 observed within the time frame specified above will be considered treatment-emergent.

Fasting glucose and nonfasting glucose (including glucose results without a known fasting status) are graded based on different grading scales as specified in the protocol.

Treatment-emergent laboratory abnormalities will be summarized for fasting glucose. Maximum postdose grade, instead of treatment-emergent grade, for nonfasting glucose (including glucose results without a known fasting status) will be summarized, as nonfasting glucose was not assessed at predose visit for most of the subjects; therefore, an abnormality is treatment-emergent or not cannot be determined for these subjects.

Both urine RBC based on microscopic examination, labeled as Hematuria (Quantitative), and urine blood based on dipstick, labeled as Hematuria (Dipstick), are assessed routinely and assigned a toxicity grade in this study. Urine RBC based on microscopic examination will be presented in laboratory toxicity summary tables and listings while urine blood based on dipstick will be presented in the listings only.

### 7.2.2.2. Summaries of Laboratory Abnormalities

Laboratory data that are categorical will be summarized using the number and percentage of subjects in the study with the given response at predose and each scheduled postdose time point.

The following summaries (number and percentage of subjects) for treatment-emergent laboratory abnormalities will be provided by lab test and cohort; subjects will be categorized according to the most severe postdose abnormality grade for a given lab test:

- Treatment-emergent laboratory abnormalities
- Treatment-emergent Grade 3 and 4 laboratory abnormalities
- Treatment-emergent Grade 2, 3, and 4 laboratory abnormalities

For all summaries of laboratory abnormalities, the denominator is the number of subjects with any nonmissing postdose values up to the minimum of (1) 30 days after Part 1 last dose date, and (2) Part 2 first dose date (if applicable).

A by-subject listing of all treatment-emergent laboratory abnormalities and treatment-emergent Grade 3 or 4 laboratory abnormalities will be provided by subject ID number and visit in chronological order. This listing will include all test results that were collected throughout the study (including Part 2) for the lab test of interest, with all applicable severity grade displayed.

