#### **Part 1:**

##### **Sentinel Cohort 1 (GS-9131 60 mg plus Current Failing Regimen)**

Following Screening and Day 1 (baseline) visits, subjects will be required to visit the clinic daily on Days 2-11. All study medication will be delivered by DOT on Days 1-10.

Laboratory analyses (hematology, chemistry, and urinalysis) will be performed at Day 1 (baseline), Day 7, and Day 11. A fasting metabolic profile will be performed on Day 1. Urine and serum pregnancy test (females of childbearing potential only) will be done at Screening and Day 1 and a urine pregnancy test on Day 11; positive urine pregnancy test on Day 11 will be confirmed with a serum pregnancy test. CD4 T cell count will be performed at Screening, Day 1 (baseline), and Day 11. A plasma sample for phenotypic and genotypic testing of HIV-1 resistance will be collected at Screening, Day 1, and Day 11. A complete physical examination will be performed at Screening, Day 1 (baseline), and Day 11. Symptom driven physical exam will be performed on Day 2 and Day 7. ECGs will be performed at Screening, Day 1, and Day 11.

On Day 10, all subjects will participate in a PK evaluation.

Samples for HIV-1 RNA will be collected at Screening, Day 1 (baseline), and Days 2, 3, 7, 10, and 11.

Assessments of adverse events (AEs) and concomitant medications will be performed at each visit.

**Sentinel Cohort 2 (GS-9131 180 mg plus Current Failing Regimen) and Randomized Cohort (GS-9131 or PTM plus Current Failing Regimen)**

Following Screening and Day 1 (baseline) visits, all study medication will be delivered by DOT on Days 1-14.

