Laboratory analyses (hematology, chemistry, and urinalysis) will be performed at Days 1 (baseline), 3, 5, 7, 10, 14, and 15. A fasting metabolic profile will be performed on Day 1. Urine and serum pregnancy test (females of childbearing potential only) will be done at Screening and Day 1 and a urine pregnancy test on Days 10 and 14; positive urine pregnancy test will be confirmed with a serum pregnancy test. CD4 T cell count will be performed at Screening and Days 1 (baseline), 10, 14, and 15. A plasma sample for phenotypic and genotypic testing of HIV-1 resistance will be collected at Screening and Days 1, 10, 14, and 15. A whole blood sample for genotypic testing of HIV-1 resistance will be collected at Day 1. A complete physical examination will be performed at Screening and Days 1 (baseline), and 14. Symptom driven physical exam will be performed on Days 2 and 7. ECGs will be performed at Screening, Day 1 and Day 15.

On Day 14, all subjects will participate in a PK evaluation.

Samples for HIV-1 RNA will be collected at Screening and Days 1 (baseline), 3, 7, 10, 14, and 15.

Assessments of AEs and concomitant medications will be performed at each visit.

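### SAP 7.2.2.2 tabulates any-time worst-grade lab abnormalities by dose cohort with 2 scheduled on-treatment draws at 60 mg and 6 at 180 mg, so the expected percentage is higher at 180 mg even without a dose effect

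*SAP*

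**What the plan says.** The lab schedule differs between the two sentinel cohorts. SAP 1.2 states for Sentinel Cohort 1 (60 mg): "Laboratory analyses (hematology, chemistry, and urinalysis) will be performed at Day 1 (baseline), Day 7, and Day 11". For Sentinel Cohort 2 (180 mg) it states: "Laboratory analyses (hematology, chemistry, and urinalysis) will be performed at Days 1 (baseline), 3, 5, 7, 10, 14, and 15". SAP Table 3-2, titled "Predose and Postdose Visits for Laboratory Tests (Hematology, Chemistry, and Urinalysis), and Vital Signs", lists the same days, and so does the protocol synopsis. Part 1 dosing lasts 10 days in Cohort 1 and 14 days in Cohort 2.

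SAP 7.2.2.1 defines a treatment-emergent abnormality by "values that increase at least 1 toxicity grade from predose at any posedose time point". SAP 7.2.2.2 says that the summaries "for treatment-emergent laboratory abnormalities will be provided by lab test and cohort", and that "subjects will be categorized according to the most severe postdose abnormality grade for a given lab test". On the percentage base, "the denominator is the number of subjects with any nonmissing postdose values up to the minimum of" two dates: 30 days after the last Part 1 dose and the first Part 2 dose. SAP 7.2.1 makes plain that cohort stands for dose: "Descriptive statistics will be provided by Cohort (different dose of GS-9131) for each laboratory test specified in the study protocol as follows".

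Nothing in the SAP limits these tables to visits that both cohorts share, adjusts for the number of draws or days observed, or cautions the reader about the difference.

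**The concern.** A worst grade over several draws rises with the number of draws. When one column takes the worst of six and the other the worst of two, the percentages do not have the same observation basis, and the denominator (any subject with at least one post-dose value) does nothing to correct this. The longer dosing period in Cohort 2 pushes the same way.

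The stake is interpretation. The study stopped before the Randomized Cohort yielded efficacy data (SAP 6), and safety tables cover only the Part 1 sentinel cohorts (SAP 7.7). So 60 mg against 180 mg is the only dose contrast that will be tabulated, and protocol 1.8.1 says that 180 mg had no clinical safety data. Readers will take these tables as information on dose-related laboratory safety. On the any-time tables alone, they cannot separate dose from sampling intensity.

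**Working it through.** **Draw count.** Post-dose visits in SAP Table 3-2: Cohort 1, Days 7 and 11, k = 2. Cohort 2, Days 3, 5, 7, 10, 14 and 15, k = 6. SAP 1.2 and the protocol synopsis agree.

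**Assumptions.** The documents give neither the per-draw probability p of a graded rise nor the within-subject correlation ρ. Both are assumed, over a range, and set equal in the two cohorts (no dose effect).

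**Formulas.**
- Independent draws: P(at least one) = 1 − (1 − p)^k.
- Correlated draws (beta-binomial): a = p(1 − ρ)/ρ, b = (1 − p)(1 − ρ)/ρ, and P(at least one) = 1 − product over i = 0 to k − 1 of (b + i)/(a + b + i).

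**Scheduled draws, 2 against 6, p = 5%.** At ρ = 0: 1 − 0.95² = 9.8%, and 1 − 0.95⁶ = 26.5%. At ρ = 0.5, a = 0.05 and b = 0.95, so for k = 2 the result is 1 − 0.95 × 1.95/2 = 7.4%.

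| ρ | 60 mg (k = 2) | 180 mg (k = 6) | Ratio |
|---|---|---|---|
| 0 | 9.8% | 26.5% | 2.7 |
| 0.2 | 8.8% | 18.4% | 2.1 |
| 0.5 | 7.4% | 11.7% | 1.6 |
| 0.8 | 6.0% | 7.3% | 1.2 |

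At p = 10% and ρ = 0 the pair is 19.0% against 46.9%, a ratio of 2.5.

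**Draws outside Table 3-2.** SAP Appendix 3, item 6, admits every graded post-dose result up to 30 days after the last Part 1 dose and before Part 2, and SAP 3.8.2 admits unscheduled visits. Subjects who do not meet the response criterion are due an early study drug discontinuation (ESDD) visit and a 30-day follow-up (protocol 6.10.1 and 6.4.2), both with blood and urine samples. Adding one of each for everyone gives 4 against 8:

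| ρ | 60 mg (k = 4) | 180 mg (k = 8) | Ratio |
|---|---|---|---|
| 0 | 18.5% | 33.7% | 1.8 |
| 0.5 | 10.1% | 12.9% | 1.3 |

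**Chance in small cohorts.** Take 11 subjects at 60 mg (protocol 1.2.3.3) and 10 at 180 mg (the planned maximum), scheduled draws only, p = 5%, no dose effect. For a given test, the probability that the 180 mg percentage exceeds the 60 mg percentage is 0.88 at ρ = 0 and 0.63 at ρ = 0.5. With two draws in each cohort it would be 0.51 and 0.46. Ties and the unequal cohort sizes explain why these are not exactly one half.

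**Matched draws.** With k = 2 in both cohorts, the no-effect expectation is equal: 9.8% against 9.8% at p = 5%, ρ = 0.

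**The case against.** A reader might infer that 180 mg must look worse by construction, on three times as many looks. The documents do not support that.

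- **Three to one is too high for what the tables contain.** Only one Cohort 1 subject is reported to have entered Part 2 (protocol 1.2.3.3), and four subjects did so in all (SAP 2.4). Suppose 10 enrolled in Cohort 2, the other three Part 2 subjects came from it, and every non-continuing subject attended both extra visits. Mean draws are then 2 + 2 × 10/11 = 3.8 against 6 + 2 × 7/10 = 7.4, a ratio near 2. The ±6-day window for the follow-up visit may put some of those draws past the 30-day cut-off. This objection stands; it shrinks the imbalance but does not remove it.
- **Independence is the least plausible case.** Days 14 and 15 are adjacent, and every draw is graded against the same predose value. This also stands: at correlation 0.8 the inflation is only about 1.2-fold.
- **Direction holds only in expectation.** At p = 5% on scheduled draws, the expected counts per test are about 1.1 of 11 against 2.7 of 10 with independent draws, or 0.8 against 1.2 at correlation 0.5. The observed table can go the other way.
- **The analysis is descriptive and the any-time definition comes from protocol 8.6.3.** SAP 7.2 plans no test, so type I error is not at issue. Percentages set out by dose still need a comparable observation basis.
- **By-visit views exist.** Numeric values and changes (SAP 7.2.1) and categorical lab results (opening of SAP 7.2.2.2) are summarized by visit, so Day 7 can be compared directly. The three treatment-emergent grade tables, however, are specified only over all post-dose draws.
- **Erring towards more abnormalities at the less-studied dose is cautious.** That is so for detection, but it does not help a reader judge whether a difference is due to dose.
- **Some rows are not affected.** The fasting metabolic profile is scheduled in Part 1 only on Day 1, so fasting lipids and fasting glucose have no scheduled post-dose Part 1 draw. Non-fasting glucose is shown as maximum post-dose grade and is affected.

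**Conclusion.** The point holds as a matter of interpretation. With equal per-draw risk, the tables in SAP 7.2.2.2 have a higher expected percentage at 180 mg with no dose effect, unless a subject's draws are perfectly correlated. At p = 5% the inflation is about 1.2- to 2.7-fold on scheduled draws (correlation 0.8 to 0). It is about 1.3- to 1.8-fold if each subject adds one ESDD and one follow-up draw (correlation 0.5 to 0). The counts of 2 and 6 are exact; p and the correlation are assumptions. It does not follow that the observed 180 mg column will look worse, or that any difference seen would be spurious. It follows only that these tables cannot attribute a difference to dose. The 10- against 14-day dosing period is a second, separate difference in the same direction.

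**What to change.** In SAP 7.2.2.2:

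1. Keep the any-time worst-grade tables, labelled as description within each cohort.
2. Add one treatment-emergent graded-abnormality table limited to matched scheduled draws: Days 7 and 11 for Sentinel Cohort 1, Days 7 and 10 for Sentinel Cohort 2. State that it is an exception to Appendix 3, item 6, so that unscheduled, ESDD and follow-up results do not enter. Pairing Day 11 with Day 10 also roughly matches days on drug. Pairing Day 11 with Day 15 would equalize draws but leave 10 against 14 days of dosing in the comparison.
3. Footnote all of these tables with the number of post-dose draws and the days observed per cohort.

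The cost is SAP wording and one filtered table from existing data. The small downside is that the matched table omits abnormalities seen only at the other Cohort 2 visits, including Days 14 and 15; these stay in the any-time tables and listings.
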